This is a Parallel Treatment study with 2 arms that is Investigator, Sponsor, and Participant blinded.

Number of Participants:

A total of approximately 60 participants will be randomized in the study.

Intervention Groups and Duration:

This study will have approximately 60 adults 18 to 50 years of age, randomized 1:1 to receive either PF-06651600 or placebo.

There will be three treatment periods, and an observation period as follows:

Treatment Period 1 (TP1) and Treatment Period 2 (TP2):

The total duration of participation in TP1 plus TP2 is approximately 26 months. This includes up to a 5-week screening period, a 9-month placebo-controlled treatment phase (TP1), a 15-month active therapy extension phase (TP2), and a 4-week follow-up period (if not proceeding to TP3) (See Section 1.2). Screening will occur within 35 days prior to Day 1 of the study to confirm that selection criteria for the study are met. At Month 9, the placebo-controlled phase will end, and all participants may enter the active therapy extension phase of the study and receive PF-06651600.

At Month 6, any participant with a baseline overall SALT score ≤ 75 will have the option to enter the active therapy extension phase if the overall SALT score at Month 6 has increased from baseline by ≥ 25 points.

At the time of their Month 15E visit, participants will have the opportunity to enter TP3, as described below. In this case, the Follow-up visit will be completed at the end of their participation in TP3.

Treatment Period 3 (TP3):

- TP3 will be of variable length for individual participants; assuming a participant does not require discontinuation per protocol, a participant may continue to receive study intervention in TP3 for a maximum of an additional 36 months or until availability of commercial product in their country, or until the Sponsor terminates the study in that country, whichever occurs first.
- In TP3, participants will receive 50 mg QD of PF-06651600. The total duration of participation in TP3 is approximately 37 months, including up to 36 months of study intervention and a Follow-up period of 4 weeks after completion or discontinuation of study intervention (See Section 1.2 Schema).

Observation Period:

[figure not shown]

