Exploratory	
 • There are no exploratory efficacy endpoints included in this CSR

Supplementary CSR 1 (Month 15E; TP2)	
Endpoint	Statistical Analysis Methods
Primary	
 • There are no primary efficacy endpoints.
Secondary	
 • For PGI-C response in the active therapy extension phase, number, and percentage with 95% confidence interval (based on Clopper-Pearson method) by initial treatment group will be presented based on observed data. • For overall and AA SALT score in the active therapy extension phase, descriptive statistics will be presented by initial treatment group. Observed data will be used.
Exploratory	
 • There are no exploratory efficacy endpoints included in this CSR.

Supplementary CSR 2 (Month 51E; TP3)	
Endpoint	Statistical Analysis Methods
Primary	
 • There are no primary efficacy endpoints.
Secondary	
 • There are no secondary efficacy endpoints included in this CSR.

Supplementary CSR 2 (Month 51E; TP3)	
Endpoint	Statistical Analysis Methods
Exploratory	
 For PGI-C response in TP3, number, and percentage with 95% confidence interval (based on Clopper–Pearson method) by initial treatment group will be presented based on observed data. For overall and AA SALT score in TP3, descriptive statistics will be presented by initial treatment group. Observed data will be used.

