9.4.3. Safety Analyses

The safety analyses will be summarized by initial treatment group in the safety population based on observed data. The baseline is defined as the last measurement before the first dose in the placebo-controlled phase.

All standard safety summary such as the incidence of safety events will be summarized by the initial treatment group for the placebo-control phase, the active therapy extension phase and TP3 extension phase. For initial active group, the overall summary for the whole study duration will also be provided.

PCD CSR (Month 9; TP1)	
Endpoint	Statistical Analysis Methods
Primary	
 The primary endpoint is change from baseline in I-V interwave latency on BAEP at Month 9. It will be analyzed using linear mixed-effects model with baseline, treatment group, visit (Months 6 and 9) and treatment group by visit interaction as fixed effects, and subject as a random effect with unstructured covariance matrix assumption. For participants who switch to the active therapy extension phase at Month 6, only their data through Month 6 will be included in the analysis of the placebo-controlled period. The estimated means, with their standard errors and 95% confidence intervals based on the model will be presented.
Secondary	
 Change from baseline in I-V interwave latency on BAEP during the placebo-controlled phase will be analyzed using linear mixed-effects model with baseline, treatment group, visit (Months 6 and 9) and treatment group by visit interaction as fixed effects, and participant as a random effect with unstructured covariance matrix assumption. The estimated means, with their standard errors and 95% confidence intervals based on the model will be presented. For data in the active therapy extension phase, descriptive statistics will be presented. For change from baseline in IENFD at Month 9 and Month 15E and change from baseline in axonal dystrophy in skin punch biopsies at Month 9 and Month 15E: descriptive statistics will be presented. Change and percent change from baseline in amplitude of wave V: the same method linear mixed-effect model as

PCD CSR (Month 9; TP1)	
Endpoint	Statistical Analysis Methods

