**Table 4. Groups**

Period	Groups
Placebo-controlled phase (TP1)	
 
• Ritlecitinib 200/50 mg QD
 
• Placebo
 

Active therapy extension phase (TP2)	
 
• Ext Ritlecitinib 50 mg QD
 
• Ext Ritlecitinib 200/50mg QD
 

Overall (TP1+TP2+TP3+Observation period)	
 
• Ritlecitinib 200/50/50 mg QD
 
• Any Ritlecitinib
 
• Any Ritlecitinib + Placebo (Total)
 

- For all the other tables, groups will be:
  - Ritlecitinib 200/50/50 mg QD
  - Placebo → Ritlecitinib 200/50 mg QD.

### 8.3. Supplemental CSR 2

The supplemental CSR 2 will be focused on safety and efficacy data from TP3 and will be prepared after the last participant completes the last visit or discontinues from the study.

- Disposition date of TP2 (or of 4 weeks follow-up period if participants didn't enter TP3) will be used to identify records in TP2 and TP3.
- All safety data in TP3, regardless of whether participants are in the Observation Period or not, will be included in summary tables.
- Only one group “All participants” including all participants will be used in all summaries.
- Efficacy data of participants while in the Observation Period will not be included in summary tables that present TP3 data by visit. Instead, listings and plots may be provided.

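### SAP 8.3 pools all TP3 participants where the protocol splits them by initial treatment group, so the TP3 report cannot show separately those with about five years on ritlecitinib

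*SAP*

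**What the plan says.** SAP Section 8.3 governs supplemental CSR 2. It defines one display group, *All participants*, and says that this group "including all participants will be used in all summaries". The SAP sections on methods and efficacy endpoints (5.2, 6.3.1, 6.3.2) call for descriptive statistics in TP3 without naming groups, so they do not restore a split.

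The protocol plans otherwise:

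- Section 9.4.2, hair loss: "For overall and AA SALT score in TP3, descriptive statistics will be presented by initial treatment group".
- Section 9.4.2, PGI-C response in TP3: counts and percentages with exact intervals "by initial treatment group will be presented based on observed data".
- Section 9.4.3, safety incidence: it "will be summarized by the initial treatment group for the placebo-control phase, the active therapy extension phase and TP3 extension phase".
- Section 9.4.3 adds: "For initial active group, the overall summary for the whole study duration will also be provided".

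The SAP version history (Table 1) ties the new Section 8 to protocol amendment 2 and describes it as setting out timing and endpoints for each report. It does not mention pooling, and the amended protocol keeps the split. For supplemental CSR 1, SAP Section 8.2 keeps the initial groups apart.

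**The concern.** The two documents give different table shells for the same report, and nothing tells the reader which was intended or why.

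The difference has content. Both randomised groups take the same drug in TP3, but one group started it a whole placebo-controlled phase earlier. Extension visits are numbered from the start of TP2 for everyone, so a visit label such as Month 51E stands for two different lengths of treatment. Protocol Section 2.3 says the study will extend the benefit-risk evaluation to as much as five years, and only the initial-ritlecitinib group can reach that. Time on drug may matter for efficacy too: Protocol Section 2.2.2.2 reports further improvement from Week 24 to Week 48 in the Phase 2b/3 study.

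The promised whole-study summary for the initial active group is also left without a report. The Overall columns of CSR 1 do isolate that group, but only up to the CSR 1 data cut-off. CSR 2 has no column for it.

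**Working it through.** **Inputs**

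- TP1 lasts 9 months and TP2 lasts 15 (Protocol 1.1).
- TP3: "a participant may continue to receive study intervention in TP3 for a maximum of an additional 36 months" (Protocol 1.1).
- Day 1E is the start of TP2 for both initial groups (Protocol 1.3.2.2; SAP Appendix 1 counts from the first extension dose).
- Some participants may enter TP2 at Month 6 (Protocol 4.1).
- Protocol 4.3 gives a maximum of 60 months for those going on to TP3.

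**Reproducing the plan's figure.** 9 + 15 + 36 = 60 months. This is the total for the initial-ritlecitinib group only. For the initial-placebo group the maximum is 15 + 36 = 51 months.

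**Exposure at visit nE.** Initial ritlecitinib = TP1 length + n. Initial placebo = n.

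| TP3 visit | Initial ritlecitinib, 9 + n | Initial placebo, n | Gap (months) | Ratio |
|---|---|---|---|---|
| 21E | 30 | 21 | 9 | 1.43 |
| 27E | 36 | 27 | 9 | 1.33 |
| 33E | 42 | 33 | 9 | 1.27 |
| 39E | 48 | 39 | 9 | 1.23 |
| 45E | 54 | 45 | 9 | 1.20 |
| 51E | 60 | 51 | 9 | 1.18 |

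**How firm the 9 months is**

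- By target days: 270 / 30.4375 = 8.9 months.
- With the 21-day extension of the end-of-placebo window: 291 / 30.4375 = 9.6 months. With the 60-day public-emergency window: 330 / 30.4375 = 10.8 months.
- An initial-ritlecitinib participant who switched at Month 6 has 6 + n months: 27 against 21 at Month 21E, and 57 against 51 at Month 51E, a gap of 6.
- If a share q of that group switched early, the mean gap is 9 − 3q months. The documents do not give q. At q = 10% the gap is 8.7 months, and at 30% it is 8.1.

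**What splitting costs in precision.** TP3 enrolment is not given, so totals of 60, 40 and 20, divided equally, are assumed. The 95% Clopper-Pearson half-widths at a 50% response are:

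| TP3 total | Pooled | Each group after splitting |
|---|---|---|
| 60 | 0.13 | 0.19 |
| 40 | 0.16 | 0.23 |
| 20 | 0.23 | 0.31 |

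The pooled interval remains available if the total column is kept.

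**The case against.** Several arguments on the other side carry weight.

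- **The SAP may depart from the protocol.** Protocol Section 9 and SAP Section 2 both allow it, and only major changes to the primary endpoint or its analysis need an amendment. A reader might infer a prohibited deviation, but the documents do not support that. What stands is an unexplained change that the version history does not record.
- **The main comparisons are intact.** A reader might infer that pooling erases the study's only designed contrast in exposure. It does not. TP1 is reported by randomised group in the PCD-CSR, and the initial groups stay separate through Month 15E in CSR 1. BAEP and skin biopsy are not scheduled in TP3. A TP3 split compares people who reached Month 15E and lacked commercial access, so it is no longer a protected randomised comparison.
- **Adverse event time at risk is not distorted.** Under SAP 3.6.1 the TP3 risk period opens at the first TP3 dose for everyone. Pooling leaves prior exposure unlabelled and nothing more.
- **On-drug and off-drug safety are not simply merged.** The sentence in SAP 8.3 that brings in all TP3 safety data, in or out of the Observation Period, could be read that way. SAP 3.6.1, however, gives CSR 2 separate adverse event summaries for the TP3 and Observation Period risk periods. Protocol 7.1.1.1 limits Observation Period visits to SALT, PGI-C and concomitant treatments, with adverse events under the usual reporting rules. SAP 8.3 keeps off-drug efficacy out of the by-visit tables. All that is left is to align the two SAP sections.
- **TP3 efficacy is exploratory and untested, and columns will be small.** True, but this argues for keeping a total column, not for dropping the groups.

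**Conclusion.** The inconsistency is real. One pooled group in every CSR 2 summary does not deliver what Protocol 9.4.2 and 9.4.3 set out for TP3, and no planned report gives the initial active group's whole-study summary through the end of TP3. The pooled by-visit columns mix nominal exposures 9 months apart, 43% more at Month 21E and falling to 18% more at Month 51E.

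The figure assumes full-length phases, uninterrupted dosing and entry to TP2 at Month 9. It is 6 months for early switchers from the initial-ritlecitinib group, and somewhat over 9 if the end-of-placebo window was stretched.

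Nothing in the documents shows that 9 further months, on top of at least 21, changes any TP3 result. The point is therefore about what a descriptive report can show, not about bias in a test or in the primary endpoint. It is still worth correcting before CSR 2, because a five-year exposure statement needs the five-year group to be visible and the change costs little.

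**What to change.** In SAP Section 8.3:

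1. Present CSR 2 efficacy and safety by initial treatment group, with *All participants* kept as a total column.
2. Add the summary for the initial active group over the whole study, through the end of TP3, and name the report that will carry it.
3. Align the sentence on including all TP3 safety data with the separate TP3 and Observation Period risk periods in SAP 3.6.1, by cross-reference.
4. Log the change in the version history.

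If the sponsor prefers to pool, the SAP should say so, give the reason, and report cumulative exposure by initial group.

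The cost is two more columns per table. Protocol 6.3.1 unblinds initial assignments once everyone has finished TP2, so no new data are needed. The downside is small columns of selected continuers, which should be read descriptively.

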## 9. ENDPOINTS INCLUDED IN EACH CSR

Efficacy analysis

PCD CSR (Month 9; TP1)	
Endpoint	Endpoints
Primary	
 
• There are no primary efficacy endpoints.
 

Secondary	
 
• PGI-C response
 
• Overall and AA SALT.
 

Exploratory	
 
• There are no exploratory efficacy endpoints included in this CSR
 

Supplementary CSR 1 (Month 15E; TP2)	
Endpoint	Statistical Analysis Methods
Primary	
 
• There are no primary efficacy endpoints.
 

Secondary	
 
• PGI-C response
 
• Overall and AA SALT
 

Exploratory	
 
• There are no exploratory efficacy endpoints included in this CSR.
 

Supplementary CSR 2 (Month 51E; TP3)	
Endpoint	Statistical Analysis Methods
Primary	
 
There are no primary efficacy endpoints.
 

Secondary	
 
There are no secondary efficacy endpoints included in this CSR.
 

Exploratory	
 
PGI-C response
 
Overall and AA SALT score
 

Safety

PCD CSR (Month 9; TP1)	
Endpoint	Statistical Analysis Methods
Primary	
 
Change from baseline in I-V interwave latency on BAEP at Month 9
 

Secondary	
 
Change from baseline in I-V interwave latency on BAEP at Month 6
 
Change from baseline in IENFD at Month 9
 
Change from baseline in percentage of IENF with axonal swellings in skin punch biopsies at Month 9
 
Change and percent change from baseline in amplitude of wave V at Months 6 and 9
 
Absence of wave V on BAEP at Months 6 and 9
 
The incidence rates of safety events, significant clinical abnormalities, vital signs and ECG
 

Supplementary CSR 1 (Month 15E; TP2)	
Endpoint	Statistical Analysis Methods
Primary	
 
There are no primary safety endpoints included in the supplemental CSR 1.
 

Secondary	
 
Change from baseline in I-V interwave latency on BAEP
 
Change from baseline in IENFD
 
Change from baseline in percentage of IENF with axonal swellings from skin punch biopsies
 
Change and percent change from baseline in amplitude of wave V
 
Absence of wave V on BAEP
 
The incidence rates of safety events, significant clinical abnormalities, vital signs and ECG
 

Supplementary CSR 2 (Month 51E; TP3)	
Endpoint	Statistical Analysis Methods
Primary	
 
There are no primary safety endpoints included in the supplemental CSR 2.
 

Secondary	
 
Incidence rates of safety events, significant clinical abnormalities and vital signs
 

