Non-AA SALT			X (see Note)	X					X	Only participants with other known etiologies of scalp hair loss in addition to AA. See Section 8.1.2.1.1 . Note: Assessment at Month 6 is required only for those eligible participants who enter the active therapy extension phase at Month 6 (See Section 4.1).
C-SSRS	X	X	X	X	X	X	X	X	X	See Section 8.2.11.1 .
Patient reported outcomes										
PGI-C	X	X	X	X	X	X	X	X	X	See Section 8.1.3.1 .

Procedure	Intervention Period									Notes
	TP1: Placebo-controlled Phase			TP2: Active Therapy Extension Phase						
Visit Identifier	3	4	5	6	7	8	9	10	11	Visit 6 (Month 9/EOP), the last visit of the placebo-controlled phase, is also the first visit of the active therapy extension phase.
Visit (Months)	1	3	6	9 / EOP	3E	6E	9E	12E	15E	E=Active Therapy Extension Phase Note: Those participants who enter the active therapy extension phase at Month 6 (Visit 5) are to complete at that visit all Month 6 (Visit 5) assessments and then follow the schedule of visits in the active therapy extension phase starting with Month 3E,
Day	31	91	181	271	91E	181E	271E	361E	451E	Day relative to the start of the study phase (ie, Day 1 = start of Placebo-controlled Phase; Day 1E = start of Active Therapy Extension Phase).
Visit Window (±Days)	±3	±7	±7 (See Note)	±7 (See Note)	±7	±7	±7	±7	±7	Note: For the EOP visit only (Month 6 or Month 9/EOP, as appropriate), the window for audiological/BAEP central read (including any repeat assessments if deemed necessary by the central reader) is -7/+21 days. All other assessments, including the primary audiological/BAEP assessments, must be completed within ±7 days.
Other										
Prior and current concomitant medication(s) and treatment(s) monitoring	X	X	X	X	X	X	X	X	X	See Section 6.5 .
Adverse event monitoring	X	X	X	X	X	X	X	X	X	See Section 8.3 and Section 10.3 .
Contraception check for WOCBP	X	X	X	X	X	X	X	X	X	See Section 5.3.1 and Section 10.4 .

Abbreviations: AA = alopecia areata; BAEP = brainstem auditory evoked potential; CRF = case report form; C-SSRS = Columbia Suicide Severity Rating Scale; ECG = electrocardiogram; EOP = End of placebo-controlled phase/ beginning of active therapy extension phase; EOT = End of Treatment; HBcAb = hepatitis B core antibody; HBVDNA = hepatitis B viral deoxyribonucleic acid; IENFD = intraepidermal nerve fiber density; IRT = Interactive Response Technology; PGI-C = Patient’s global impression of change; SALT = Severity of Alopecia Tool; WOCBP = women of childbearing potential.

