HBVDNA (applicable countries)	X	X	X(see Note)	X	X	X	Only for participants who were enrolled with a positive HBcAb and a negative HBVDNA in those regions for which hepatitis B prevalence has been reported at a rate of >5.0% or if required by local standard of care. Testing at additional time points may be performed as per the local standard of care. See Section 8.2.10.3 , Section 10.2 , and Section 10.6 .
Tuberculosis testing		X		X		X	See Section 8.2.10.1 , Section 8.2.3 , and Section 10.2 .
IRT study intervention assignment							IRT will be contacted at Month 15E for participants entering Extension Phase TP3 for study intervention assignment.
Study intervention dispensing	X	X	X	X	X	X	The participant will return the package containing the study intervention which was dispensed at the previous visit for accountability. See Section 6.2 .

Procedure	Intervention Period						Notes
Phase:	TP3: Extension Phase						
Visit Identifier	12	13	14	15	16	17/EOT	
Visit (Months)	21E	27E	33E	39E	45E	51E	Note: Those participants who enter Extension Phase TP3 at Month 15E (Visit 11) are to complete at that visit all Month 15E (Visit 11) assessments and then follow the schedule of visits in Extension Phase, starting with Month 21E (Visit 12).
Day	631E	811E	991E	1171E	1351E	1531E	Day relative to the start of the study phase (Day 1E = start of Active Therapy Extension Phase TP2)
Visit Window (±Days)	±7	±7	±7	±7	±7	±7	
Study intervention administration	X	X	X	X	X		See Section 6.1 .
Study intervention accountability and compliance	X	X	X	X	X	X	See Section 6.2 and Section 6.4 .
SALT	X	X	X	X	X	X	See Section 8.1.2.1 .
Non-AA SALT						X	Only participants with other known etiologies of scalp hair loss in addition to AA. See Section 8.1.2.1.1 .
C-SSRS	X	X	X	X	X	X	See Section 8.2.11.1 .
PGI-C	X	X	X	X	X	X	See Section 8.1.3.1 .
Prior and current concomitant medication(s) and treatment(s) monitoring	X	X	X	X	X	X	See Section 6.5 .
Adverse event monitoring	X	X	X	X	X	X	See Section 8.3 and Section 10.3 .
Contraception check for WOCBP	X	X	X	X	X	X	See Section 5.3.1 and Section 10.4 .

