The proportion of participants who experienced all-causality TEAEs was similar across treatment groups up to Week 24 (placebo-controlled period) and up to Week 48 (overall). The most frequently reported TEAEs in any group included nasopharyngitis, headache, and upper respiratory tract infection. Up to Week 24, the incidence of nasopharyngitis, folliculitis, urticaria, dizziness, and urinary tract infection was higher in participants treated with PF-06651600 (particularly 200/50 mg and 200/30 mg) than placebo. Most TEAEs were mild to moderate in severity. Fourteen (14) participants experienced 16 SAEs up to Week 48.

- 200/50 mg (4 participants): appendicitis; empyema and sepsis; invasive lobular breast carcinoma, spontaneous abortion
- 200/30 mg (2 participants): appendicitis; chemical poisoning and suicidal behavior
- 50 mg (2 participants): breast cancer; pulmonary embolism
- 30 mg (1 participant): diverticulitis
- 10 mg (2 participants): suicidal behavior; eczema
- Placebo-200/50 mg: no SAEs
- Placebo-50 mg (3 participants): spontaneous abortion; conversion disorder; heavy menstrual bleeding. These treatment-emergent SAEs were all reported during the Placebo-Controlled Period.

All SAEs were considered by the investigator as unrelated to study drug, except in 3 participants (sepsis and empyema, breast cancer, eczema). There were no deaths reported in the study.

Treatment with PF-06651600 was associated with changes in hematological parameters, some of which were dose dependent. From Week 4 onward, there were slight, transient decreases in hemoglobin and small, variable changes in neutrophil and leukocyte levels. Small, early decreases in platelets were observed with PF-06651600 treatment; these levels remained stable up to Week 48. Dose-dependent early decreases in absolute lymphocyte levels, CD3 (T lymphocytes) and T lymphocyte subsets (CD4 and CD8) were observed. Up to Week 24, there was a dose-dependent early decrease in CD16/56 (NK cells), particularly in groups who had received a 200 mg loading dose of PF-06651600 for 4 weeks. Overall, there were no clinically meaningful effects of PF-06651600 on ALT, AST, bilirubin, or alkaline phosphatase. The incidence of elevation in hepatic enzymes was low and not dose dependent. Up to Week 48, there were no potential Hy's law cases.

For a complete description and results of this study, please refer to the current version of the PF-06651600 IB.

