8.2.11. Suicidal Ideation and Behavior Risk Monitoring

8.2.11.1. Columbia Suicide Severity Rating Scale (C-SSRS)

There are 2 versions of the C-SSRS to be utilized in this study - “C-SSRS for screening and Day 1 visits” and “C-SSRS for any visits after Day 1”⁽⁵⁴⁾. The version used is dictated by the actual study visit and the participant population (See the SoA [Section 1.3]).

At the screening or Day 1 visits, if the participant has had suicidal ideation associated with actual intent and a method or plan in the past year (“yes” answers on items 4, 5), the participant will not be included in the study. For participants, suicidal behavior in the past year (“Yes” answer on any question in the suicidal behavior section of the C-SSRS), is exclusionary. For participants who have had previous history of suicidal behaviors in the past >1 year, (a “Yes” answer to any of the suicidal behavior items of the C-SSRS), a risk assessment must be performed and documented by a qualified mental health professional to assess whether it is safe for the participant to participate in the trial.

Any participants who are not eligible due to suicidal ideation or behavior should be referred for appropriate evaluation and treatment.

For all participants with suicidal ideation associated with actual intent and a method or plan in the past year: At any visits after Day 1, if there are “yes” answers on items 4, 5, or on any question in the suicidal behavior section of the C-SSRS, the participant will be discontinued from the study and referred to a mental health professional for appropriate evaluation and treatment or immediately referred to the Emergency Room at the investigator’s judgement.

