## 1. VERSION HISTORY

**Table 1. Summary of Major Changes in SAP Amendments**

Version/ Date	Associated Protocol Amendment	Rationale	Specific Changes
1.0 05 Aug 2020	Original 8 May 2020	Not Applicable	Not Applicable
2.0 28 Sep 2021	Amendment 1 20 Apr 2021	To match TLF	Add abbreviations to the analysis set
		For clarification	In section 5.2, elaborate the “Binary safety data”
		To assess the impact of COVID-19	In section 6.7, add COVID-19 related safety analysis
		For clarification	Add appendix 2, list of countries for regions
		For clarification	Add details to calculate cumulative dose/compliance by visit in Section 6.6.3 and appendix 3
		ECG analysis was missing in version 1	Add ECG analysis in Section 6.2.9
		For clarification	Added details to calculate cumulative dose and compliance in appendix 3.
		For clarification	In section 7, specified only data up to Month 9 will be included in the analysis for PCD
3.0 22 Nov 2021	Amendment 1 20 Apr 2021	For clarification	In section 7, update the scope of PCD CSR, and unblinding/blinding status of sponsors, investigators and participants after PCD
		For clarification	In section 3.6.3, specified that only QTcF interval will be analyzed, instead of all ECG parameters
		Team decision	Delete the analysis of physical examinations, C-SSRS, and cumulative dose up to each visit
4.0 17 Aug 2022	Amendment 2 28 Apr 2022	Updated to incorporate changes in protocol amendment 2	In section 2, updated the study objects and endpoints, study design

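### The C-SSRS is collected at every treatment visit but has no table or listing in any study report, so below-threshold ideation not recorded as an adverse event is never tabulated and the C-SSRS discontinuation criterion is never counted

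*SAP*

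**What the plan says.** **Collection.** Protocol 8.2.11.1 states: "There are 2 versions of the C-SSRS to be utilized in this study". One form serves screening and Day 1; the other serves all later visits. The schedules in Protocol 1.3 mark the scale at screening, Day 1, all nine TP1 and TP2 visits, all six TP3 visits and Early Termination. Protocol 5.2 excludes on it. Protocol 8.2.11.1 and 10.7.2 require discontinuation for a positive item 4 or 5 or any positive behavior item.

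**Analysis.** The SAP defines no C-SSRS endpoint in section 3 and plans no C-SSRS summary in sections 5, 6, 8 or 9. In section 9 the general safety entry is "The incidence rates of safety events, significant clinical abnormalities, vital signs and ECG" for the PCD CSR and supplemental CSR 1, and "Incidence rates of safety events, significant clinical abnormalities and vital signs" for supplemental CSR 2. The only mention of the scale is in Table 1, under version 3.0: "Delete the analysis of physical examinations, C-SSRS, and cumulative dose up to each visit". The rationale column says only that the team decided it. The current text agrees with that entry, so the deletion is in force.

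**Comparable criteria.** SAP 6.7.2 and 8.1 plan summaries of participants meeting the laboratory discontinuation criteria and of QTcF values meeting pre-specified criteria.

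**Background.** Protocol 2.2 describes depression and anxiety as frequent in AA. Protocol 2.2.2.2 lists, among SAEs in the Phase 2b/3 AA trial, "200/30 mg (2 participants): appendicitis; chemical poisoning and suicidal behavior" and "10 mg (2 participants): suicidal behavior; eczema".

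**The concern.** This is a safety study with a blinded, randomised nine-month placebo phase. The C-SSRS puts the same fixed items to every participant in both arms, whereas AEs come from open-ended questioning followed by the investigator's decision to record. With no C-SSRS summary, the reports can say what was recorded as an AE. They cannot say how many participants were assessed, how many gave any positive ideation answer, or how many worsened from baseline. The plan is also uneven: Protocol 10.7.2 places the C-SSRS criterion in the same list as the laboratory and QTcF criteria, yet only the latter two are counted.

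**Working it through.** The plan gives no figure for the C-SSRS, so the check sets collection against reporting and then sizes the gap.

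**1. Scheduled assessments** (Protocol 1.3.2.1 and 1.3.2.2)
- TP1: Months 1, 3, 6, 9 = 4
- TP2: Months 3E, 6E, 9E, 12E, 15E = 5
- TP3: Months 21E, 27E, 33E, 39E, 45E, 51E = 6
- Total post-baseline: 4 + 5 + 6 = 15 per participant. This is a maximum. Participants who switch at Month 6 skip Month 9 (Protocol 4.1), TP3 varies in length, and the Observation Period does not collect the scale (Protocol 7.1.1.1).
- Randomised, blinded part: 4 x 60 = 240 scheduled assessments at most.

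**2. Where a positive answer can go under the current SAP**
- *Items 4 or 5, or any behavior item:* the participant is discontinued. If recorded as an AE, the event appears among TEAEs and AEs leading to discontinuation (SAP 6.2.6 to 6.2.8). No table counts participants meeting the C-SSRS criterion itself.
- *Lower ideation items, recorded as an AE:* counted in the TEAE tables, by arm in TP1 (SAP 6.2.6, and Tables 3 and 4).
- *Lower ideation items, not recorded as an AE:* no table. No rule requires such an answer to be recorded. In the telehealth instructions (Protocol 10.9.2), clinically significant audiological and neurological changes are sent to the AE form; the C-SSRS bullet gives only the discontinuation and referral step.

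**3. Do the general statements reinstate it?** SAP 6.7 promises to list and summarise safety endpoints, and the C-SSRS is not defined as one. SAP 8.1 and 8.2 speak of including all safety data, but name no C-SSRS output and cannot be read as restoring an analysis that was expressly deleted.

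**4. The earlier trial.** The SAE list adds up to its stated totals: participants 4 + 2 + 2 + 1 + 2 + 0 + 3 = 14; events 5 + 3 + 2 + 1 + 2 + 0 + 3 = 16. Suicidal behavior accounts for 2 participants. Against the 715 treated (Protocol 2.2.2), 2/715 = 0.28% (exact 95% interval 0.03% to 1.01%). Neither is among the three participants whose SAEs were judged related.

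**5. What a TP1 table could show, with 30 per arm.** For 0 events in n, the exact (Clopper-Pearson) upper bound is 1 - 0.025^(1/n).

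| Positive / assessed | Exact 95% interval |
|---|---|
| 0/30 | 0 to 11.6% |
| 1/30 | 0.1% to 17.2% |
| 2/30 | 0.8% to 22.1% |
| 3/30 | 2.1% to 26.5% |

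The documents give no ideation rates. Under assumed rates, two-sided 5% Fisher power is about 9% for 5% versus 15%, 24% for 5% versus 20%, and 63% for 5% versus 30%.

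**The case against.** The strongest reply is that the C-SSRS is here a tool for protecting individual participants. It serves eligibility and discontinuation and appears in no endpoint list. Protocol section 9 lets the SAP modify the plan, and the deletion was logged openly. All of this stands: no protocol endpoint was dropped, and a one-line log entry without a scientific reason does not prove the choice wrong.

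Three stronger readings are tempting, and the documents do not support them.

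- *That ideation which does not stop treatment goes wholly unreported, or that only spontaneous reports count.* AEs are actively elicited (Protocol 8.3 and 8.3.1), clinically significant findings on other safety assessments meet the AE definition (Protocol 10.3.1), and TEAEs are shown by arm in TP1. Only answers not recorded as AEs are missing.
- *That some 900 assessments (15 x 60) are lost to a by-arm comparison.* All participants receive active drug after TP1, and supplemental CSR 2 uses one pooled group (SAP 8.3). The randomised part is at most about 240.
- *That the earlier SAEs are a drug signal.* Both were judged unrelated. They arose at 200/30 mg and 10 mg, not on the regimen studied here, and the protocol gives no per-arm denominators to set against placebo. They show that the topic is relevant, no more.

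The low power is real too. It argues for a descriptive table with intervals, in keeping with a SAP that tests no hypothesis. It does not argue for no table.

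**Conclusion.** The point holds in limited form. A safety assessment scheduled up to 15 times per participant after baseline, 4 of them under randomised blinding, has no planned table or listing in any of the three reports. The loss is confined to positive answers below items 4 and 5 that are not recorded as AEs, to the count of participants meeting the C-SSRS discontinuation criterion, and to the number assessed. The by-arm loss concerns TP1 only. How many answers are affected cannot be derived, because the documents give no ideation rates and do not say how often sites record such answers as AEs. The primary endpoint, its precision and the clinical rules are untouched. This is a worthwhile, inexpensive reporting improvement, not a defect that threatens the study's conclusions.

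**What to change.** In SAP 6.7, 8 and 9, restore one descriptive C-SSRS table and a listing of positive cases.

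- **Supplemental CSR 1 (or the PCD CSR if still open):** for TP1 by arm, and for TP2 by the groups in SAP Table 4, give the number assessed and the number and percentage with any post-baseline ideation (items 1 to 5), with items 4 or 5, and with any suicidal behavior. Add exact 95% intervals for TP1, and a shift from the worst screening or Day 1 category to the worst post-baseline category, noting that different forms are used before and after Day 1.
- **Supplemental CSR 2:** the same table for the single pooled group.
- **Number assessed:** show it in every table. During public emergencies the scale is required at telehealth visits (Protocol 10.9.2) but cannot be given at home visits (10.9.6).
- **Labelling:** the SAP log for version 4.0 describes analyses as already added to the PCD CSR, so that report appears to have been prepared, and Protocol 6.3.1 has sponsor staff unblinded after the PCD. A TP1 table added after that point should be labelled post hoc.

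If the sponsor prefers to keep the deletion, the SAP should state the scientific reason. The cost is a little programming on data already collected, with sparse counts and wide intervals to present. No clinical rule changes.
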